The mixed blinded solutions will be provided to the investigator/nursing staff for administration. If not used immediately, the IMP combined with Lactated Ringer's solution should be stored under refrigerated conditions and must be administered within 24 hours of preparation. Doses may be given at 8 AM within +/- a 2-hour window for the AM dose and 12 hours after the AM dose +/- a 3-hour window for the PM dose. The clinical site staff should consult with the Medical Monitor about any missed dose outside the allowable dosing window. Typically, these missed doses should be given and documented following standard procedure.

All patients will receive a total of 13 doses of drug product or placebo across 7 days of treatment (a single morning dose will be given on Day 7). All doses should be given using strict aseptic techniques and may be administered by clinic/hospital staff provided they have been given adequate training. Upon completion of the study, patients requiring subsequent catheterization should have their study catheter replaced. The catheter used in the study should be discarded per normal site policy.

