#### 3.4.3 *Pharmacokinetic Concentration*

LBP-EC01 concentrations will be determined in both blood and urine by using a plaque forming assay and expressed in units of plaque forming units (PFU)/mL.

Actual sampling times that are outside the sampling time windows may be excluded from concentration summary and mean concentration plotting but will still be used in the calculations of PK parameters and individual concentration plotting.

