### 3.5 Pharmacodynamic Assessment

The secondary endpoints concern the pharmacodynamics of LBP-EC01. These will be summarized by treatment based on the PD Population.

*E. coli* assessments will be made at the timepoints specified in the SoA of the protocol. Incidence of the following endpoints will also be summarized with counts and percentages of patients at Day 1 (Baseline), Day 2, Day 3, Day 5, Day 7 (EOT), Day 14 and Day 28:

- Reduction in urinary *E. coli* burden at timepoint from Baseline
- Biological elimination of *E. coli* at timepoint after Baseline. Biological elimination is defined as measurement below  $1 \times 10^3$  CFU/mL

The following *E. coli* parameters will be derived based on all available post-Baseline data and summarized and listed:

- Time to 1 log reduction in urinary *E. coli* from Baseline
- Biological elimination at any timepoint.
- Incidence and time to recurrence of *E. coli* colonization. Recurrence is defined as past biological elimination followed by increase above the patient's baseline CFU/mL.
- Incidence of infection based on clinical signs and symptoms defined as an adverse event marked as a UTI symptom and followed by antibiotic use.

*E. coli* parameters will be summarized first for the total CFU/mL in a patient (sum of CFU/mL for all *E. coli* strains) but may also be summarized by strain specific *E. coli* colonization (individual strain CFU/mL per patient).

All *E. coli* assessment data will be listed.

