##### 3.6.2.1 *Phage Sensitivity/Resistance*

Phage sensitivity and resistance by *E. coli* isolates will be collected at the timepoints specified in the SoA of the protocol. Incidence of the following will be summarized by isolate for the cocktail and each individual phage:

- Isolates that yield ennumerable plaques (PFU/mL)
- Isolates that yield ennumerable plaques (PFU/mL) or that demonstrate “lysis from without”
- Insensitive isolates (no ennumerable plaques or no “lysis from without”)

All phage sensitivity and resistance will be listed by patient for each *E. coli* isolate, including *E. coli* sensitivity to the cocktail and to each individual phage.

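### Any-timepoint elimination, time to 1-log reduction and recurrence pool cultures taken during phage dosing with later ones, so one low on-treatment reading can count as clearance, with a possible specimen artefact in the active arm only

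*SAP*

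**What the plan says.** Section 3.5 of the SAP states that the E. coli "parameters will be derived based on all available post-Baseline data and summarized and listed". The parameters under that rule include "Time to 1 log reduction in urinary" E. coli from baseline, "Biological elimination at any timepoint", and the incidence and time to recurrence. Recurrence requires an earlier elimination followed by a rise above the patient's own baseline count.

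The criterion is one reading: "Biological elimination is defined as measurement below" 1x10^3 CFU/mL. No confirmatory culture is required. The post-baseline visits are "Day 2, Day 3, Day 5, Day 7 (EOT), Day 14 and Day 28". The same section also tabulates reduction and elimination at each of these visits by treatment, and lists all E. coli data.

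On dosing, Section 2.2.3 says "All patients will receive a total of 13 doses of drug product or placebo across 7 days of treatment". It describes placebo as Lactated Ringer's solution. On phage in urine, Section 3.4.3 says "LBP-EC01 concentrations will be determined in both blood and urine by using a plaque forming assay", and Section 3.4.4 defines urine trough and post-dose maximum parameters through Day 7. Section 3.6.2.1 classifies isolates by their response to phage in the laboratory, including the category "Isolates that yield ennumerable plaques (PFU/mL) or that demonstrate" lysis from without.

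**The concern.** A plaque assay detects infectious phage, and the SAP plans to measure it in urine through Day 7. A culture taken in that period from an LBP-EC01 patient with a sensitive strain may therefore reflect two things: killing in the bladder, which is the effect of interest, and killing that continues in the container or on the plate after collection. Placebo specimens hold no study phage, so any such artefact acts on one arm only.

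The pooled derivations do not separate these cultures from those at Days 14 and 28. An any-timepoint rule takes the most favourable of six readings, so errors in one direction accumulate. A false elimination also enlarges the group at risk of recurrence in the active arm, which could count against the product. Time to 1-log reduction takes the earliest qualifying reading, and four of the six opportunities are on treatment. What is at stake is how the secondary activity results are read; no hypothesis is tested (Section 3.1.5).

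**Working it through.** **Inputs from the SAP.** Six post-baseline culture visits (3.5); dosing on Days 1 to 7, 13 doses (2.2.3); product titre 1x10^6 to 1x10^12 PFU/mL, 15 mL per vial mixed with 45 mL diluent (2.2.3); 36 patients randomized 2:1, so 24 and 12 (2.2.4).

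**Assumptions, not in the SAP.** Phage adsorption rate k from 10^-10 to 10^-8 mL/min; chance q per on-treatment visit that specimen killing alone gives a count below 10^3; background chance b of a low reading per visit.

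**1. Visits within dosing.** Days 2, 3, 5 and 7 are within dosing and Days 14 and 28 are after it: 4 of 6.

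**2. The plan's own figure.** Vial content = titre x 15 mL = 1.5x10^7 to 1.5x10^13 PFU, as Section 2.2.3 states. Instilled titre = vial content / 60 mL = 2.5x10^5 to 2.5x10^11 PFU/mL. Urine at sampling would hold less after drainage and dilution.

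**3. Can killing in the specimen matter?** Time to a 1-log fall = ln(10) / (k x P), where P is the phage titre in the specimen.

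| P (PFU/mL) | k = 10^-8 | k = 10^-10 |
|---|---|---|
| 2.5x10^5 | 921 min | 92,103 min |
| 10^8 | 2.3 min | 230 min |
| 2.5x10^11 | under 0.1 min | under 0.1 min |

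If 1% of the lowest instilled titre remained, P = 2.5x10^3. Even at the fastest rate the time is 2.303 / (10^-8 x 2.5x10^3), about 92,000 min or 64 days, which is negligible. The answer therefore runs from no effect to an almost immediate one across the stated titre range.

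**4. Accumulation over four on-treatment visits.** With no true effect and no background, the probability of at least one false elimination is 1 - (1 - q)^4 if visits are independent, and q if they are fully correlated.

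| q | Independent | Fully correlated |
|---|---|---|
| 0.05 | 18.5% (4.5 of 24) | 5% (1.2 of 24) |
| 0.10 | 34.4% (8.3 of 24) | 10% (2.4 of 24) |
| 0.20 | 59.0% (14.2 of 24) | 20% (4.8 of 24) |

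Repeated cultures from one patient and strain are unlikely to be independent, so both columns are needed.

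**5. With background in both arms.** Take b = 0.05, independent visits and no true effect.
- Placebo, any timepoint: 1 - 0.95^6 = 26.5%.
- LBP-EC01, q = 0.10: 1 - (0.95 x 0.90)^4 x 0.95^2 = 51.8%.
- LBP-EC01, q = 0.20: 1 - (0.95 x 0.80)^4 x 0.95^2 = 69.9%.
- Days 14 and 28 only, either arm: 1 - 0.95^2 = 9.8%, provided no phage persists after dosing.

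These figures show how the rule behaves if the artefact exists. They do not estimate how often it occurs.

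**The case against.** The strongest reply is that the artefact depends on two facts not in this document: when culture urine is taken relative to a dose, and whether the laboratory removes or neutralizes phage before plating. Section 3.5 refers to the protocol for timepoints, and plating method is laboratory procedure that a SAP need not contain. The solution is drained after 30 to 40 minutes, so a pre-dose specimen could hold far less phage than a post-dose one. Appendix A specifies a pre-dose specimen, but for dipstick and microscopy. Sections 3.4.3 and 3.6.2.1 describe the concentration assay and isolate testing; neither shows that culture counts are lowered by carry-over. All of this stands, and it limits the point to a risk.

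Much of the protective information is also already planned: Day 14 and Day 28 elimination by arm, and listed urine phage concentrations (Section 3.4.3). A time-to-event value also shows its own day. That mitigates the pooling, but it does not supply an off-treatment version of recurrence or a combined off-treatment elimination row.

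A reader might infer more: that active-arm elimination rates are inflated, that any-timepoint elimination is the main activity result, or that off-treatment definitions should replace the present ones. The SAP supports none of these. It gives no data on carry-over. Section 2.3.2 does not name any-timepoint elimination among the secondary endpoints. On-treatment reduction is itself a specified effect there, and a recurrence rule confined to off-treatment elimination would leave only the interval from Day 14 to Day 28 among scheduled visits, missing a patient cleared by Day 7 and above baseline at Day 14.

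**Conclusion.** The point holds as a weakness in the derivation rule. The three derived parameters mix on-treatment and off-treatment cultures, a single unconfirmed reading decides elimination, and the possible specimen artefact is confined to the LBP-EC01 arm. Nothing in the SAP separates or guards against it in these parameters.

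The size is unknown. The illustrations rest on assumed values of q, b and k and on the assumed correlation between visits. At q of 5% to 20% they run from 5% to 59% false any-timepoint elimination, and q may be close to zero if urine titres are low or specimens are handled to control carry-over. The harm would be to the reading of descriptive secondary results, not to any error rate. The change is worth making because it is cheap and uses data already collected.

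**What to change.** In Section 3.5, before treatment assignments are unblinded (Section 5.2), keep the current derivations and add:

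- (a) Any-timepoint elimination shown separately for on-treatment cultures (Days 2 to 7) and off-treatment cultures (Day 14 or Day 28), with statements about sustained clearance resting on the off-treatment row.
- (b) Incidence and time to recurrence shown both from any elimination and from an off-treatment elimination.
- (c) Time to 1-log reduction labelled as reached on or off treatment, and listed beside the same-visit urine PFU/mL where available.

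If sampling time or laboratory handling already controls phage carry-over, a sentence in Section 3.5 citing it would largely answer the concern.

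The cost is some SAP wording and a few extra table rows, with no new data. The off-treatment recurrence row will rest on small numbers. Days 14 and 28 are also not guaranteed to be phage-free, so the off-treatment rows reduce the risk without removing it.

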### 2.3.2 Secondary Endpoints

The secondary endpoints involve summarizing PD parameters of LBP-EC01. These include:

- Reduction in urinary *E. coli* burden at any of the following timepoints: Day 2, Day 3, Day 5, Day 7 (EOT), Day 14, and Day 28
- Time to 1 log reduction in urinary *E. coli* count
- Recurrence of *E. coli* colonization or incidence of infection based on clinical signs and symptoms
- Changes in IgA, IgE, IgG, and IgM levels

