### 3.2.5 *PD Population*

The PD Population is defined as all randomized patients who met enrollment criteria, who receive at least one dose of study drug, have a baseline PK assessment, and have a baseline *E. coli* measurement at or above  $1 \times 10^3$  Colony-Forming Unit (CFU)/mL. The PD Population will be the primary population for analysis of all PD-related secondary and exploratory endpoints.

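### Recurrence of E. coli requires a total count above the patient's own baseline, so a full return to baseline after elimination is recorded as no recurrence

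*SAP*

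**What the plan says.** Section 2.3.2 names recurrence of E. coli "colonization or incidence of infection based on clinical signs and symptoms" among the secondary endpoints. Section 3.5 makes it operational with two definitions:

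- Elimination: "Biological elimination is defined as measurement below" 1×10^3 CFU/mL.
- Recurrence: "Recurrence is defined as past biological elimination followed by increase above the patient's baseline CFU/mL".

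Section 3.5 also reports "Biological elimination at any timepoint", and says that the E. coli "parameters will be derived based on all available post-Baseline data and summarized and listed". These parameters are summarized first on the patient's total count over all strains. A summary by strain ("individual strain CFU/mL per patient") is optional.

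Section 3.2.5 admits patients to the PD Population only with a baseline E. coli "measurement at or above" 1×10^3 CFU/mL. Section 3.1.1 defines baseline as the last value before first dose, which is a single measurement.

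The SAP gives no other recurrence rule. Section 2.3.3 mentions recurrent E. coli under urine culture but does not define it.

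**The concern.** Elimination is judged against a fixed count, recurrence against the patient's own starting count. The two thresholds never coincide in a way that counts a plain return to baseline, and for any baseline above 1×10^3 they leave a gap. A previously eliminated patient whose total count climbs back into that gap has lost elimination, yet stays in the eliminated-at-any-timepoint figure and is not recurrent.

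The endpoint is meant to describe colonization coming back, and 1×10^3 CFU/mL is the count the SAP itself uses to decide who enters the PD analysis. The rule as written measures overshoot beyond baseline instead. The report could then pair a favourable elimination figure with a recurrence figure that omits complete recolonization.

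The infection parameter does not fill the gap. It is "defined as an adverse event marked as a UTI symptom and followed by antibiotic use", so it misses a return of colonization without symptoms, in a study whose population includes patients with asymptomatic bacteriuria (section 2.2.1).

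**Working it through.** The SAP gives no figure to reproduce here, so the check applies its rules as written. All counts below are illustrative, because the SAP gives no distribution of E. coli counts.

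**Inputs**
- Eliminated at a timepoint: count < 10^3 (section 3.5).
- Recurrent: an earlier count < 10^3 and a later count > baseline (section 3.5).
- Total-count baseline ≥ 10^3 (section 3.2.5).
- Comparison rule: an earlier count < 10^3 and a later count ≥ 10^3.

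**Step 1: worked cases on total counts (CFU/mL)**

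| Baseline | Lowest | Later | log10(later/baseline) | Eliminated at later visit | Recurrent, SAP | Recurrent, ≥10^3 |
|---|---|---|---|---|---|---|
| 10^3 | 10^2 | 10^3 | 0.000 | no | no | yes |
| 10^3 | 10^2 | 2×10^3 | +0.301 | no | yes | yes |
| 10^6 | 10^2 | 2×10^3 | −2.699 | no | no | yes |
| 10^6 | 10^2 | 5×10^5 | −0.301 | no | no | yes |
| 10^6 | 10^2 | 9×10^5 | −0.046 | no | no | yes |
| 10^6 | 10^2 | 10^6 | 0.000 | no | no | yes |
| 10^6 | 10^2 | 1.1×10^6 | +0.041 | no | yes | yes |

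The SAP rule counts two of the seven returns as recurrence; the comparison rule counts all seven. At every baseline tried from 10^3 to 10^7, a rebound to 100% of baseline is no recurrence and a rebound to 101% is.

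**Step 2: width of the uncounted band**

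The band runs from 10^3 up to and including baseline, so its width is log10(baseline) − 3. That is 0 at a baseline of 10^3 (the single value 10^3), 1 at 10^4, 2 at 10^5, 3 at 10^6 and 4 at 10^7.

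**Step 3: ordering of patients**

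The path 10^3 → 10^2 → 2×10^3 is a recurrence and 10^6 → 10^2 → 10^6 is not, although the second final count is 10^6 / (2×10^3) = 500 times higher.

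**Step 4: dependence on measurement noise (illustrative)**

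Assume that every eliminated patient returns fully to the original level, that baseline and the k later counts are exchangeable, and that there are no ties. Baseline is then the largest of the k + 1 values with probability 1/(k + 1), so the SAP rule records recurrence with probability k/(k + 1): 1/2 = 50%, 2/3 = 67% and 3/4 = 75% for k = 1, 2 and 3, whatever the within-patient variance. Complete recolonization in everyone would thus give a recorded rate set by noise and by the number of later samples. This is not an estimate for this trial.

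**Step 5: optional strain-specific summaries**

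Section 3.2.5 does not bound each strain's baseline, so here the rule can fail the other way. A strain going 200 → 100 → 300 is eliminated (300 < 10^3) and recurrent (300 > 200) at the same timepoint.

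**The case against.** The strongest reply is that this is an open, programmable definition that nothing else in the SAP contradicts. Section 7 reports no departure from the protocol apart from the COVID-19 additions, so the rule may come from the protocol, with a rationale not visible here. A stringent rule may have been intended, and incidence is too low only relative to another standard. Part of this stands: the definition is clear, and the precise complaint is that it does not count regrowth up to baseline. But the other standard is the SAP's own 1×10^3 threshold, and the SAP gives no reason for leaving it.

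Second, any measure relative to baseline can order patients differently from their absolute counts, so step 3 alone proves little. That is fair. It illustrates the effect of pairing an absolute elimination rule with a relative recurrence rule; the case rests on steps 1 and 2.

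Third, section 3.5 also tabulates elimination and reduction by visit and lists all counts, so unsustained elimination can be seen. This helps in part. By-visit counts are marginal: they do not separate patients who lost elimination from those who never reached it. The reduction row states no minimum size, so 9×10^5 against a baseline of 10^6 may still appear as a reduction. A reader would have to rebuild recurrence from the listings.

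Fourth, the stakes are limited. No hypothesis is tested (section 3.1.5). With 36 patients at 2:1, there are about 24 and 12 per arm, and only those who first reach elimination can recur. This stands, and it caps the seriousness of the point. In a purely descriptive report, though, the definition fixes the number that is read.

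**Conclusion.** The concern holds and should be fixed. Following section 3.5 exactly, a total count that returns from below 1×10^3 to any value up to and including baseline is never a recurrence. The incidence of this secondary endpoint omits such patients, and their time to recurrence is delayed or never reached.

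The uncounted band is log10(baseline) − 3 logs wide. That result needs only the two definitions and the PD Population's minimum baseline. The particular baselines shown are illustrative.

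The share of recurrences missed and the direction of any difference between arms cannot be determined: the SAP gives no count distribution, and the sampling schedule is in the protocol. The strain-level problem is secondary, because those summaries are optional.

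**What to change.** Before database lock and unblinding:

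1. Derive recurrence, both its incidence and its time from first biological elimination, as a return to ≥1×10^3 CFU/mL after elimination, on the total count.
2. Keep the above-baseline rule as a second row, labelled as such.
3. As a helpful addition, show returns during treatment separately from returns after it. Split at the end of treatment (section 3.1.2) rather than by named visits, so that all available post-baseline data are kept.
4. If strain-specific summaries are produced, limit recurrence to strains with a baseline of at least 1×10^3 CFU/mL.
5. Record the change in section 7 if the protocol carries the present definition.

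The cost is a wording change, one added derivation and an extra labelled table row, plus the period split if adopted. No new data are needed. The downside is a higher reported recurrence rate and some sensitivity to noise at the threshold: 9×10^2 followed by 1.0×10^3 would count. The retained row and the period split make that visible but do not remove it.

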which the patient may be released from the clinic/hospital. The patient will return on Day 14 ( $\pm 3$  days) for the Day 14 Visit, and on Day 28 ( $\pm 3$  days) for the Day 28 Visit. AE data will be collected throughout the study, including Day 28 through Day 35. At Day 35, the patient will be contacted by telephone to assess any AEs or lab abnormalities since the Day 28 Visit. At the discretion of the investigator, the patient may be asked to return to the clinic/hospital for a Day 35 Visit ( $\pm 3$  days). Day 35 is the end of study. Assessments will be conducted as described in Table 1 and Table 2 of the Protocol.

Safety will be assessed throughout the study. Spleen evaluations will include ultrasound assessments for splenomegaly at Day -6 to -1, Day 3, and Day 7 and clinical examinations to assess for splenomegaly will be performed at all visits. In addition, attention will be focused on identifying any progression of a urinary colonization to an active infection, including the signs and symptoms of local vesicular reactions (e.g., bladder pain, hematuria). Symptoms of active infection will be solicited during daily observations throughout the 7 days of treatment and until the end of study. Symptoms of note in this population include dysuria, urinary frequency, urinary urgency, suprapubic discomfort and flank pain in addition to non-specific symptoms of urinary leakage, change in voiding habits, worsening muscle spasm, increasing autonomic dysreflexia, sweating, malaise, and fever or hypothermia. Urine microscopy and culture will be assessed frequently during the study (see Table 2 of the Protocol).

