### *3.1.3 End of Study Definition*

A patient is considered to have completed the study if he or she has completed all portions of the study including the last visit or the last scheduled procedure shown in the SoA (Table 1 of the Protocol).

The EOS is defined as the last date that patient safety data is collected (i.e., Day 35). Once patients have completed Day 28, they may resume their regular medications and have any new intermittent catheters re-established as directed by their physician.

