### 3.3.4 Demographic and Baseline Characteristics

The following demographic and baseline characteristics will be summarized:

- Age (years) at enrollment
- Sex
- Childbearing potential
- Race
- Ethnicity
- Height (cm)
- Weight (kg)
- Body mass index (BMI) (kg/m^2)
- Frequency and timing (within 1 month of Screening, within 1 year of Screening) of prior UTI
- Prior antibiotic use (within 30 days of Screening)
- Catheter use at Screening (none, indwelling, intermittent, other)

Demographic and baseline characteristics will be summarized with descriptive statistics or counts and percentages of patients as appropriate by treatment and in total for all randomized patients and each defined analysis population. Data will also be listed.

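### The infection endpoint in SAP 3.5 does not require the antibiotic to be given for the urinary symptom, so an antibiotic for an unrelated reason can count as an infection

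*SAP*

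**What the plan says.** SAP section 2.3.2 lists among the secondary endpoints recurrence of *E. coli* "colonization or incidence of infection based on clinical signs and symptoms". Section 3.5 turns the infection part into a derivation rule, with infection "defined as an adverse event marked as a UTI symptom and followed by antibiotic use". The same section says that these "parameters will be derived based on all available post-Baseline data and summarized and listed".

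Follow-up for events is long compared with the 7-day treatment period. Section 2.2.1 states that "AE data will be collected throughout the study, including Day 28 through Day 35", and section 3.1.3 puts the end of study at Day 35.

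Section 3.3.6 sorts medications into prior and concomitant by their dates relative to the first dose. It does not mention indication or any link to an adverse event. Section 3.7.1 makes UTI signs and symptoms adverse events of special interest, but does not connect them to treatment.

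**The concern.** The rule needs two things: a flagged urinary symptom, then an antibiotic. It does not say that the antibiotic must be treatment for that symptom, and it sets no interval between the two. Suppose a patient has brief dysuria on Day 3 that settles untreated, and later in follow-up takes an antibiotic for a chest or skin infection. That patient satisfies both conditions and is counted as a urinary infection.

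This is more than a detail left open. Section 3.5 gives a definition that looks complete, and a programmer who follows it exactly would classify that patient as infected. The endpoint is meant to show progression from colonization to infection, a matter to which section 2.2.1 directs particular attention. In arms this small, one or two wrong classifications would visibly change the reported incidence.

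**Working it through.** The SAP states no infection rate, alpha, power or effect size, so there is no figure of the plan to reproduce. The check has two parts.

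**1. Does any other section supply the missing link?**

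| SAP section | What it adds | Link between antibiotic and symptom? |
|---|---|---|
| 3.5 | Flagged symptom, then antibiotic; all post-Baseline data | Order only |
| 2.2.1 | Symptoms solicited and events collected to end of study | None |
| 3.1.3 | End of study at Day 35 | None |
| 3.2.3 | Patients who progress to active infection stop study treatment and are treated for their symptoms | Describes treatment for symptoms, but does not define this endpoint |
| 3.3.6 | Medications classified by date | None |
| 3.7.1 | UTI signs and symptoms as events of special interest | None |

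Section 3.5 points to the protocol for assessment timepoints, but for infection it gives its own definition and refers to nothing else. The literal rule therefore stands as written.

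**2. How much does one misclassified patient weigh?**

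Inputs: 36 patients randomized 2:1 (section 2.2.4). Assumption: all of them enter the PD Population, the population named in section 3.5.

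- LBP-EC01: 36 × 2/3 = 24 patients; one patient = 1/24 = 4.2 percentage points.
- Placebo: 36 × 1/3 = 12 patients; one patient = 1/12 = 8.3 percentage points.

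The PD Population also requires that enrollment criteria were met, a baseline PK assessment, and a baseline count of at least 1 × 10³ CFU/mL (section 3.2.5). If that removes patients from an arm, each remaining patient weighs more.

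**Expected number of false cases.** This would need two quantities that the SAP does not give: the share *s* of patients with a UTI-symptom event that is not an infection, and the chance *a* of a later unrelated antibiotic. The false-infection rate is *s* × *a* if the two are independent. With purely assumed ranges of *s* = 0.2 to 0.6 and *a* = 0.1 to 0.4:

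- lowest: 0.2 × 0.1 = 2%, or 36 × 0.02 = 0.7 patients;
- highest: 0.6 × 0.4 = 24%, or 36 × 0.24 = 8.6 patients.

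That range is too wide to support any estimate. The firm results are the 4.2 and 8.3 points per patient.

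**The case against.** **The natural reading is treatment for the symptom.** The endpoint is headed as infection based on clinical signs and symptoms, and section 3.2.3 speaks of treating patients for their symptoms. That is very probably the intent. But the derivation rule does not say so, and the rule is what will be programmed.

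**The event must carry a UTI-symptom mark.** This is a real filter. A reader might infer that everything in the solicited list, including "non-specific symptoms of urinary leakage, change in voiding habits, worsening muscle spasm, increasing autonomic dysreflexia, sweating, malaise, and fever or hypothermia", feeds the endpoint. The SAP does not say that these are all marked, so the breadth of the list does not establish how often the first condition is met.

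**The detail may sit elsewhere.** Section 8 mentions separate programming specifications, and the protocol was not available for this review. Either might narrow the rule, but section 3.5 refers to neither for this definition.

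**Little depends on it.** Section 3.1.5 rules out formal hypothesis tests, and adverse events and medications are listed in full, so each counted case can be checked by hand. This stands and limits the importance. It does not remove the case for fixing the rule before anyone sees the treatment codes.

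**Stronger readings that the SAP does not support.** A reader might join "Once patients have completed Day 28, they may resume their regular medications" with the baseline item "Prior antibiotic use (within 30 days of Screening)" and conclude that patients will restart routine antibiotics and so become infections. Section 3.1.3 does not name antibiotics, section 3.3.4 gives no rate and does not describe regular use, and that route would open only after Day 28. A reader might also take this endpoint as the trial's main clinical signal, or assume that catheter-related symptoms are frequent in both arms. The SAP supports neither: safety is a primary endpoint in its own right (section 2.3.1), and no symptom frequency is given.

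**Conclusion.** The concern holds in a limited form. Section 3.5 states a rule that can misclassify: an antibiotic given for any reason after a UTI-symptom event, up to end of study, can count as an infection. Whether this will happen, how often, and in which arm more cannot be told from the SAP, so no direction of bias is claimed.

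The size is per patient: about 4.2 points on LBP-EC01 and 8.3 points on placebo, assuming a 24 and 12 split with all patients in the PD Population. The affected result is one descriptive secondary endpoint. The primary safety and PK summaries do not depend on it. The amendment is worth making because it is short, but the point is minor.

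**What to change.** Before unblinding, amend the infection definition in section 3.5 so that an antibiotic counts only if both conditions hold:

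1. its recorded indication is UTI or the UTI-symptom adverse event, or it is recorded as treatment for that event; and
2. it starts on or after that event's onset.

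List separately the antibiotics that follow a UTI-symptom event but fail this link, and show the incidence under the current rule as a sensitivity summary, so that the effect of the change is visible.

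The definition should not also require the antibiotic to start before the event resolves. That could drop true infections, for example where treatment follows a late culture result or the event's end date is incomplete.

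**Cost:** a sentence or two in the SAP, one listing and one extra summary line. The downside is reliance on a complete indication or event-link field, which the SAP does not mention. Where it is missing, a blinded review would have to decide. That review could be completed alongside the Evaluable Population list, which section 3.2.3 already requires to be final before unblinding. The change affects classification only and leaves patient management untouched.
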